- Subjects in the SAD Level 2 Two-Dose (20mg) will be dosed in a fasting state on Day 1 with a subsequent 4-day washout period, followed by dosing in a fed state (standard not-high fat breakfast) on Day 6.
- SAD Level 4 (80 mg) dosing is optional and may be adjusted based upon PK and safety results from earlier cohorts.
- Subjects may be enrolled in small groups to accommodate clinic scheduling.

MAD Levels 1–6 dosing:

- The MAD portion of the study will commence at MAD Level 1 (10 mg) after the safe completion of the subjects in at least the 2 SAD Level 2 Two-Dose cohort.
- Subjects in MAD Levels 1–6 will be dosed in a fed state (standard non-high-fat breakfast) over 14 continuous days of dosing.
- MAD cohorts may be enrolled in small groups to accommodate clinic scheduling with subjects dosed in a staggered fashion.

Dose Escalation:

The study will be monitored by a Safety Review Committee (SRC) comprised of the Principal Investigator (PI), the Medical Monitor, and the Sponsor. The SRC is intended to ensure treatment does not pose undue risk to subjects. Dose escalation to the next higher dose level cohort will not take place until the SRC has assessed the data from at least 7 out of 8 subjects/cohort through discharge (supplemental plasma PK information on a previously treated cohort may be requested as a part of the review) and determined that adequate safety and tolerability has been demonstrated to permit proceeding.

The planned dose levels for MAD Cohort 5 (80 mg) and Cohort 6 (160 mg) may be decreased based on the plasma PK from the preceding MAD cohort. Escalation will proceed no higher than a dose that is estimated to yield $\leq \frac{1}{2}$ of the rate 28-day NOAEL exposure ($C_{\max} \leq 421$ ng/mL, $AUC_{0-24} \leq 6,600$ ng*hr/mL).

The SRC may recommend:

- Ascending to the planned next higher dose level
- Ascending to a dose level lower than the planned next higher dosage level cohort
- Repeat dosing at the current dose level
- Descending to an intermediate dose above a previously tolerated dose level
- Pausing dose escalation
- Stopping the study

Participation in the clinical study may be discontinued by an Investigator (or delegate) in charge of the study or by the Sponsor for any of the following reasons in [Table 5](#).

Table 5: Stopping Rules

Stopping Rules ^d	Individual Subject Stopping Rules ^a	Cohort and/or Dose Escalation Stopping Rules
ALT or AST $\geq 3 \times$ ULN	≥ 1 subject	N/A

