ALT or AST $> 5 \times$ ULN	N/A	≥ 2 subjects
Creatinine $> 1.2 \times$ ULN or an increase in serum creatinine by $\geq 30 \mu\text{mol/L}$ within 24 hours or an increase in serum creatinine to $\geq 1.5 \times$ baseline within 7 days	≥ 1 subject	≥ 2 subjects
QTcB and QTcF > 500 msec or change from baseline: QTc > 60 msec	≥ 1 subject	≥ 2 subjects
Sustained heart rate < 45 bpm or heart rate > 130 bpm ^b confirmed by repeat after 30 minutes	≥ 1 subject	≥ 2 subjects
Sustained systolic blood pressure < 80 or systolic blood pressure > 155 mmHg confirmed by repeat after 30 minutes	≥ 1 subject	≥ 2 subjects
Sustained diastolic blood pressure > 100 mmHg confirmed by repeat after 30 minutes	≥ 1 subject	≥ 2 subjects
Occurrence of a serious adverse event (SAE) in a participant not receiving placebo	≥ 1 subject	≥ 1 subject
Severe AEs in the same cohort	N/A	≥ 1 subject
Clinically significant laboratory abnormalities of the same character	N/A	≥ 2 subjects
Confirmed lower urinary tract obstruction ^c (Two successive post-void residual volume determinations within 24 hours exceeding 100 mL) or evidence of hydronephrosis upon Ultrasound evaluation.	≥ 1 subject	≥ 1 subjects
A drop in the eGFR below 70 mL/min/1.73 m ² (CKD-EPI) or a reduction of 25% from baseline.	≥ 1 subject	≥ 2 subjects
A confirmed ^e reduction in the FVC (forced vital capacity done in triplicate) to less than 80% of the predicted vital capacity based on gender, height and age with good expiratory effort as assessed by the Investigator	≥ 1 subject	≥ 2 subjects
Any subject who develops gross or microscopic (> 5 RBC/HPF) hematuria (unless clearly caused by menses)	≥ 1 subject	≥ 2 subjects
Any subject who has signs, symptoms, and urinalysis/dipstick evidence of a clinically significant urinary tract infection	≥ 1 subject	≥ 2 subjects

Abbreviations: AE = adverse event; ALT = alanine aminotransferase; AST = aspartate aminotransferase; bpm = beats per minute; mmHg= millimeters of mercury; msec = millisecond; IP = investigational product; N/A = not applicable; QTcB= QT correct with Bazett formula; QTcF = QT interval corrected for heart rate using Fridericia's formula ;ULN = upper limit of normal.

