7. Has clinical laboratory test results within the reference ranges of the testing laboratory, except for results outside reference ranges that are deemed not clinically significant by the Investigator (or designee) at screening and check-in to the CRU on Day -1.
8. Vital signs are within normal limits after 3 minutes resting in supine position and FVC (measured in the seated position and triplicate averaged) is $\geq 90\%$ of the predicted value for gender, age and height with good expiratory effort.

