7. Active or history of metabolic, cardiovascular, or cerebrovascular disease, including hypertension, angina, ischemic heart disease, transient ischemic attacks, bundle branch block, evidence of myocardial ischemia, stroke, and peripheral arterial disease sufficient to cause symptoms and/or require therapy to maintain stable status.
8. History of significant hypersensitivity, intolerance, or allergy to any drug compound, food, or other substance, unless approved by the Investigator (or designee).
9. Active neoplastic disease or history of any neoplastic disease within 5 years of screening (except for basal or squamous cell carcinoma of the skin or carcinoma in situ that has been definitely treated with standard of care).
10. Active infection (e.g., sepsis, pneumonia, abscess) or a serious infection (e.g., resulting in hospitalization or requiring parenteral antibiotic treatment) within 6 weeks prior to dosing.
11. History of stomach or intestinal surgery or resection that would potentially alter absorption and/or excretion of orally administered drugs (uncomplicated appendectomy and hernia repair will be allowed).

12. Any of the following at screening and/or pre-dose:
 - a. Triplicate averaged QT interval corrected for heart rate using Fridericia's formula (QTcF), QRS duration (>120 msec), PR interval (>220 msec) outside of normal limits confirmed by repeat measurement, unless deemed non-clinically significant by PI and agreed by Medical Monitor
 - b. Findings which would make QTc measurements difficult or QTc data uninterpretable
 - c. History of additional risk factors for Torsades de Pointes (e.g., heart failure, hypokalemia, family history of long QT syndrome)
13. History of alcoholism or drug/chemical abuse.
14. Unwilling to abstain from alcohol consumption within 24 hours of check-in to the CRU on Day -1 and throughout the study.
15. Positive urine drug screen (including cotinine, cannabinoids, amphetamines, cocaine, opiates, benzodiazepines, or barbiturates) at screening or check-in, or positive urine alcohol screen at check-in to the CRU on Day -1.
16. Positive hepatitis panel and/or positive human immunodeficiency virus test at screening.
17. Any of the following hematology values at screening or check-in to the CRU on Day -1, as confirmed by 1 repeat if necessary:
 - a. Hemoglobin <11 g/dL for females, and <12 g/dL for males
 - b. Absolute neutrophil count (ANC) <1.5 × 10⁹/L (<1500/μL).

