7. DISCONTINUATION OF STUDY TREATMENT, SUBJECT WITHDRAWAL, AND SUBJECT REPLACEMENT

7.1. Discontinuation of Study Treatment

A subject must be discontinued from study treatment for any of the following:

1. Withdrawal of consent to further follow-up assessments, irrespective of the reason. Note: a subject may withdraw consent to receive further study drug but should be requested to allow follow up for safety and collection of other follow up data.
2. Unable to remain under medical supervision.
3. Investigator decision (may include the need for other therapy not otherwise permitted in the study; any clinically relevant sign, symptom, or intercurrent illness that, in the opinion of the Investigator [or designee], warrants subject withdrawal).
4. Noncompliance with the study restrictions that might affect subject safety or study assessments/objectives, as considered applicable by the Investigator (or designee).
5. Change in compliance with any inclusion/exclusion criterion that is clinically relevant and affects subject safety as determined by the Investigator (or designee).
6. Has an SAE.
7. Meets any of the hepatotoxicity criteria detailed in [Table 5](#).
8. Death.

The Investigator must contact the Sponsor immediately to discuss whether to suspend dosing if an AE or laboratory abnormalities indicate that continued dosing of subsequent subjects would not be tolerated or would jeopardize the subjects' safety.

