8.3. Safety Assessments

Safety assessments ([Table 8](#)) will include AEs and SAEs, as well as physical examinations, clinical laboratory evaluations, vital sign measurements, spirometry, urinary system ultrasound, Echocardiography, and ECGs. Not every assessment will be performed at each visit. Refer to the Schedule of Assessments ([Table 1](#), [Table 2](#), and [Table 3](#)) for specific procedures/assessments and timing. A separate schedule of permitted visit windows for each procedure/assessment will be provided in the Clinical Monitoring Plan and Data Management Plan

Note: When several assessments overlap, the suggested sequence of events will be as follows: ECG, vital sign collection, PK sample collection, laboratory blood sample collections, spirometry, dynamometry, urinalysis sample collection, and biopsy such that PK sample collection will be drawn as close to the nominal collection time point as possible. Echocardiography and Urinary system ultrasounds can be performed last so as to not delay the PK assessments.

Table 8: Safety Assessments

Assessment	Details
AE monitoring	Adverse events will be recorded from the first study medication dose through 14 days after the last follow-up visit/call. AEs will be graded using the scale in Section 8.4.4.3.
Physical examination	Physical examination and review of relevant systems at screening, including body weight and height. Symptom-directed physical examinations and weight measurements are to be performed at other time points or as clinically indicated.
Neurological exam	Includes cranial nerve assessments II-XII, cerebellar function (finger to nose and gait), reflexes (bilateral bicep, patellar, and ankle), gross assessment of extremity strength.
Vital signs	Systolic and diastolic blood pressure, heart rate, respiratory rate, and body temperature.
12-lead Electrocardiograms	The QTcF must be recorded for each ECG. All ECGs must be performed in triplicate with at least a 5 minute rest in the supine position with a minimum of 60 seconds in between and the average value will be used for interpretation and AE grade.
Left ventricular ejection fraction (LVEF)/ echocardiogram	An echocardiogram will measure ventricular volumes and left ventricular ejection fraction.

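### Read literally, the QTc stopping row needs both QTcB and QTcF above 500 ms, so below 60 bpm it can miss a QTcF just above 500; its 60 ms limb names no correction (low impact)

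*Protocol*

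**What the plan says.** The row "QTcB and QTcF > 500 msec or change from baseline: QTc > 60 msec" appears with the same wording in the protocol Synopsis, in Table 5 of Section 4.1 and in SAP Section 7. One subject meeting it is grounds to stop that subject; two are grounds to stop the cohort or the escalation. No footnote says whether one correction is enough, or which correction the 60 ms change uses. The abbreviations under the table define QTcB and QTcF but not plain QTc.

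Elsewhere the plan works in QTcF. Table 8 (Section 8.3) states "The QTcF must be recorded for each ECG", and for the triplicate tracings "the average value will be used for interpretation and AE grade". Exclusion 12a (Section 5.2) uses triplicate-averaged QTcF but gives no millisecond limit for it, unlike QRS and PR. Its test is "outside of normal limits confirmed by repeat measurement, unless deemed non-clinically significant by PI and agreed by Medical Monitor". SAP Section 5.16.4 tabulates QTc, QTcB and QTcF as three separate variables.

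The lead-in to Table 5 is permissive: "Participation in the clinical study may be discontinued by an Investigator", or by the sponsor. The trial stopping rules in Section 4.1.1 contain no QTc criterion.

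**The concern.** Bazett and Fridericia agree at 60 bpm. Above that rate QTcB is the larger; below it QTcB is the smaller. A rule that needs both above 500 ms is therefore decided by QTcF at 60 bpm and above, and by QTcB below 60 bpm. At slow rates the row can answer no to a QTcF above 500, although QTcF is the correction the rest of the protocol relies on.

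The 60 ms limb should catch many of these cases, but it cannot do so when baseline QTcF is already high. Because it names no correction, two people applying it to the same tracings can also reach different answers when heart rate has shifted. At stake is a threshold for individual and cohort stopping in a first-in-human study whose remaining doses (SAD 160 mg; MAD 40, 80 and up to 160 mg) lie above those in the unblinded interim safety analysis (single doses to 80 mg, repeat doses to 20 mg; Protocol Section 2.3).

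**Working it through.** The plan states no figure to reproduce here. The documents name the two corrections without printing the formulas, so the standard definitions are used. Heart rates (HR, bpm) and baseline values are assumptions, because the documents give no distribution of either.

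**Step 1. Relation between the corrections.** With RR = 60/HR in seconds, QTcB = QT/RR^(1/2) and QTcF = QT/RR^(1/3). Hence QTcB = QTcF × (HR/60)^(1/6).

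**Step 2. QTcF needed for the literal 500 ms limb.** Both values must exceed 500, so QTcF must exceed the larger of 500 and 500 × (60/HR)^(1/6).

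| HR | QTcF must exceed | QTcF missed |
|---|---|---|
| 45 | 524.6 | 500 to 524.6 |
| 50 | 515.4 | 500 to 515.4 |
| 52 | 512.1 | 500 to 512.1 |
| 55 | 507.3 | 500 to 507.3 |
| 57 | 504.3 | 500 to 504.3 |
| 59 | 501.4 | 500 to 501.4 |
| 60 or more | 500.0 | none |

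A QTcF of 501 gives QTcB 493.8 at 55 bpm (limb not met) and 507.7 at 65 bpm (met). The table starts at 45 bpm because a sustained rate below 45 has its own stopping row.

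**Step 3. When the 60 ms limb does not rescue the case.** Read as QTcF, it stays silent if baseline ≥ on-study value − 60. With the on-study value above 500, baseline must exceed 440. At the top of the missed band the baseline must be at least 447.3 at 55 bpm (507.3 − 60) or 455.4 at 50 bpm (515.4 − 60).

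**Step 4. Worked case.** Baseline QTcF 448 at 60 bpm; on study 505 at 55 bpm.
- QTcF change: 505 − 448 = +57.
- QTcB: 448.0 at baseline, then 505 × (55/60)^(1/6) = 497.7, a change of +49.7.
- QTcF is above 500 but QTcB is not, and neither change exceeds 60. No limb fires, whichever correction the second limb uses.

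**Step 5. Effect of the entry limit.** If exclusion 12a were applied with a QTcF limit L and never waived, the upper end of the missed band would be the smaller of L + 60 and the Step 2 value. L = 440 closes the gap. L = 450 leaves 500 to 510 at 50 bpm and 500 to 507.3 at 55 bpm. Both limits are assumptions.

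**Step 6. Effect of the unnamed correction in the 60 ms limb.** Baseline QTcF 420 at 60 bpm, where QTcB is also 420:
- To QTcF 485 at 50 bpm: +65 by Fridericia (stop). QTcB = 485 × (50/60)^(1/6) = 470.5, so +50.5 by Bazett (no stop).
- To QTcF 465 at 80 bpm: +45 by Fridericia (no stop). QTcB = 465 × (80/60)^(1/6) = 487.8, so +67.8 by Bazett (stop).

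**Step 7. If the conjunction means either value.** The slow-rate gap closes, but QTcF 477 at 80 bpm gives QTcB = 477 × (80/60)^(1/6) = 500.4, which triggers on Bazett alone.

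**The case against.** The strongest reply is that the row is ambiguous rather than wrong. It can be read as a list in which each correction is held to 500 ms, and then there is no slow-rate gap. Even the joint reading has a rationale: at 60 bpm and above it equals QTcF > 500 and avoids stops caused by Bazett over-correction. The intent is not recorded, so this stands in part. Against it, the same table uses *or* for alternatives (ALT or AST; gross or microscopic hematuria) and *and* where conditions apply together (the urinary infection row). That makes the joint reading the natural one.

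A second reply is that the gap needs several things at once: a rate below 60 bpm, a QTcF only slightly above 500, a baseline above 440 and a rise of no more than 60 ms. Exclusion 12a removes some such subjects, and inclusion 8 ("Vital signs are within normal limits after 3 minutes resting in supine position") removes some with slow resting rates. This stands, with limits. 12a has no QTcF figure and can be waived; inclusion 8 governs entry, not on-study rate.

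A third reply is that other routes would catch the case, and this also stands. Section 7.1 item 3 requires discontinuation on investigator decision, which covers any clinically relevant sign. A clinically significant ECG finding is an adverse event (Section 8.4.1.1), and one severe adverse event stops a cohort. The sponsor may suspend dosing at any time, and the SRC reviews ECG data before escalation. None of these sets a numeric QTc threshold.

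A reader might infer from Section 7.1 item 7 ("Meets any of the hepatotoxicity criteria detailed in" Table 5) that only the hepatotoxicity rows bind. The section does not support that: item 6 makes an SAE, also a Table 5 row, a mandatory reason, and item 3 is broad.

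**Conclusion.** The point holds as a minor wording defect in a decision threshold. Read literally, the plan's only numeric QTc trigger does not fire for a QTcF of 500 to 507.3 ms at 55 bpm, or 500 to 515.4 ms at 50 bpm, when baseline QTcF exceeds 440 ms and the rise is at most 60 ms. The baseline condition takes the 60 ms limb as QTcF, which is the natural reading given Table 8 and exclusion 12a but is not stated.

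The impact is low. How often the gap would matter cannot be estimated, because the documents give neither a heart-rate distribution nor a QTcF entry limit. A reader might infer that a subject with QTcF above 500 would be kept on drug. The documents do not support that: the row is discretionary, the routes above remain, and the interim safety analysis reported no clinically significant ECG abnormalities at the doses it covered.

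**What to change.** In the Synopsis, Table 5 and SAP Section 7, replace the row with *QTcF > 500 msec or increase from baseline in QTcF > 60 msec*, evaluated on the triplicate mean already set in Table 8. Against the literal reading, the 500 ms limb is unchanged at 60 bpm and above and stricter below.

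There is one downside, so the sponsor should confirm its intent first. If either correction was meant to be enough, this wording drops Bazett-only triggers at faster rates, such as QTcF 477 at 80 bpm (QTcB 500.4). In that case write *QTcB or QTcF > 500 msec* for the first limb and still name QTcF for the 60 ms change.

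As optional tidying, define or delete the plain QTc variable in SAP Section 5.16.4. The cost is one row of wording in three places, with no new ECGs or analyses.

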4.1.1. Trial Stopping Rules

The Investigator must contact the Sponsor immediately to discuss whether to suspend dosing if an AE or laboratory abnormalities indicate that continued dosing of subsequent subjects would not be tolerated or would jeopardize the subjects' safety. The Sponsor alone may suspend dosing at any time for any reason.

Clinical trial stopping rules:

- Occurrence of 1 SAE in a participant not receiving placebo.
- Occurrence of 'severe' non-serious adverse reactions in a participant not receiving placebo.
- Occurrence of 1 death in a participant not receiving placebo.
- Occurrence of 1 case of lower urinary tract obstruction (by catheter-confirmed post void residuals) or hydronephrosis (by ultrasound).
- Occurrence of 2 or more subjects with gross hematuria (unless clearly caused by menses).

Occurrence of 2 or more subjects with a decrease of 50% or more in eGFR. If any of the above scenarios occur, the study will be immediately paused. Further discussion will then occur within the SRC, and a safety review will be conducted. Following the SRC review, the study may continue if the Investigator and Sponsor agree it is safe to proceed. If the study is stopped, the maximum tolerated dose (MTD) will be declared at the dose level lower than that escalation dose.

Study Assessments and Procedures Overview:

Safety assessments will include physical and neurological examinations, vital signs, ECG,

Spirometry, Echocardiography, urinary system ultrasound, and laboratory assessments. Adverse events will be collected from first dose through the follow-up telephone call (Day 7 for subjects in all SAD level cohorts; Day 12 for subjects in the SAD Level 2, Two-Dose cohort; Day 20 for subjects in all MAD cohorts).

Telemetry and digit oximetry will be monitored by applying at least 1 hour prior to dose administration and remain on for approximately 24 hours in the SAD cohorts. In MAD cohorts, telemetry and digit oximetry will be monitored for approximately 24 hours starting on Day 1, Day 7, and Day 14, and monitored on all dosing days from pre-dose until 12 hours post-dose for the duration of the study. Telemetry and oximetry will be interrupted to accommodate daily hygienic routines (e.g., showering).

Blood and urine sample collection for PK analysis of MTR-601 will be collected in the clinical research unit (CRU) at specified time points as detailed in the Schedule of Assessments ([Table 1](#), [Table 2](#), and [Table 3](#)).

Spirometry measurements will include:

- Forced expiratory volume in one second (FEV₁)
- Forced vital capacity (FVC)
- FEV₁/FVC ratio (FEV₁ divided by FVC)

Dynamometry measurements will include grip strength, upper extremity (forearm extension/flexion), and lower extremity (knee extension in sitting position).

Refer to the Schedule of Assessments ([Table 1](#), [Table 2](#), and [Table 3](#)) for details on exact days and times of assessments.

4.1.2. Study Duration

Subjects Planned:	Duration of IP for each subject by dose level cohort:		
Approximately 88	SAD: 1 day	SAD Two-Dose: 2 days	MAD: 14 days
Total study duration for each subject:			
SAD:	A (maximum) 30-day screening period, check-in to the CRU on Day -1, a single dose of study medication on Day 1 with subsequent in-house observation of at least 96 hours ^a , check-out/discharge from the CRU, and a telephone follow-up on Day 7. The total duration will be approximately 37 days.		
SAD Two-Dose:	A (maximum) 30-day screening period, check-in to CRU on Day -1, a single dose of study medication on Day 1, a 4-day washout period, a second single dose of study medication on Day 6 with subsequent in-house observation of at least 96 hours ^a , check-out/discharge from the CRU, and a telephone follow-up on Day 12. The total duration will be approximately 42 days.		
MAD:	A (maximum) 30-day screening period, check-in to the CRU on Day -1, daily dosing of study medication on Days 1–14 with subsequent in-house observation of at least 96 hours ^a after the last dose, check-out/discharge from the CRU, and a telephone follow-up on Day 20. The total duration will be approximately 50 days.		

- a. If needed (e.g., in the event of AEs), the in-house observation period may be prolonged for safety observation at the discretion of the Investigator, which will extend duration of study participation by the number of additional observation days required.

